## Background

Intravenous opioids are commonly used to treat acute abdominal pain in US emergency departments (ED). These medications are highly efficacious and, when used in a monitored setting such as the ED, extremely safe. Use of opioids has fallen out of favor because of a spike in opioid-related overdose deaths throughout the US. While use of opioids in the ED is unlikely to contribute to outpatient opioid deaths, minimizing the use of opioids in the ED will contribute to an opioid free culture, in which opioids are used only when absolutely necessary. A variety of different types of medications can be used in lieu of opioids. One such medication, intravenous lidocaine, has been used extensively in various arenas including the operating room, where it is an evidence-based preventive of post-operative pain, and the cardiac care unit, where it historically had been used to prevent arrhythmias. Some data suggest that it may be efficacious for acute abdominal pain as well.

Intravenous lidocaine has long been used to treat pain. In publications dating back to 1980, intravenous lidocaine has been shown to be an effective treatment for neuropathic pain (2). In the post-operative setting, intravenous lidocaine decreased pain and decreased the need for opiates (3-7). More recently, emergency medicine investigators in Iran, demonstrated that intravenous lidocaine decreased pain associated with renal colic and limb ischemia (9-11). An ED-based study in the US showed comparable efficacy between morphine and intravenous lidocaine when used for acute abdominal pain (12).

Over the years, intravenous lidocaine has been used for a variety of indications including arrhythmia prophylaxis in patients with acute coronary syndromes. Known side effects of intravenous lidocaine range from transient neurological symptoms (dizziness, paresthesias), to cardiac dysrhythmias and seizure. To date, no deaths have been attributed to its use for treating pain and the only documented significant complication was due to an unintentional overdose where a patient received ten times the normal dose (2, 3, 8). All reported side effects in pain patients have been transient and resolve by stopping the drug, decreasing the infusion rate, or by observation alone. Thus, intravenous lidocaine is an emerging medication for safe and rapid relief of pain, has no known addictive properties, and creates a potential for a pain practice paradigm shift in the United States.

We therefore propose a randomized, double blind, RCT to address the following aim:  
To determine the relative efficacy and safety of IV lidocaine among patients with acute abdominal pain, when compared to IV hydromorphone, the putative standard of care

## IV lidocaine v. hydromorphone for acute abdominal pain. A randomized trial. Version date 07112018

## Methods.

Study design. This will be a randomized, double blind, comparative effectiveness study conducted in two Montefiore EDs. Outcomes will be assessed through out the ED stay and by telephone 7 days later. Ethical oversight will be provided by the Montefiore Medical Center IRB. This trial will be registered online at <http://www.clinicaltrials.gov>.

Population of interest. Eligible patients are those who present to an ED for treatment of acute abdominal pain. Acute will be defined as pain for no more than seven days. At the time of enrollment, the ED treatment plan must include use of an intravenous opioid. Adults aged at least 18 years and less than 65 years will be eligible to participate. Patients will be excluded from participation if they have cardiac conduction system impairment (QTc duration > 0.5s, QRS duration > 0.12s, or PR interval duration > 0.2s), known renal (CKD >2) or liver disease (Childs-Pugh B or greater), are hemodynamically unstable, as determined by the attending physician, are pregnant or breastfeeding, or have a known allergy to either medication. Patients will also be excluded if they have used prescription or illicit opioids within the previous week, or if they have a chronic pain disorder, defined as use of any analgesic medication on more days than not during the month preceding the acute episode of pain. Patients weighing < 60kg or > 120kg will be excluded.

Study setting. This study will be conducted in the Moses and Weiler EDs.

Investigational medications. Patients will be randomized in a 1:1 ration to one of the following study arms:

- A. Lidocaine: 120mg IV
- B. Hydromorphone: 1mg IV

Each of these medications will be administered as an intravenous drip over 10 minutes. If patients report insufficient relief of pain at 30 minutes, they will be eligible for a second dose of the same medication. Thirty minutes after the investigational medication was initiated, participants will be asked, "Do you want another dose of the same medication to treat your pain?" Subjects who reply affirmatively will be administered the same medication and dose they had received thirty minutes previously. Patients who require additional medication beyond one hour will be administered medication at the discretion of the treating clinician.

Hydromorphone, dosed at 1mg + 1mg, is a safe and effective strategy for management of acute pain in the ED (<https://www.ncbi.nlm.nih.gov/pubmed/21507527>). The optimal dose of IV lidocaine for acute pain is unknown. For this study, we chose a dose that was most likely to be efficacious while minimizing potential for adverse events. A Cochrane review of intravenous lidocaine for post-operative pain reported that most trials used lidocaine boluses between 1-3 mg/kg (typically 1.5 mg/kg). ED-based studies have used doses of 1.5-2 mg/kg (8-11).

Assignment. Will be concealed. The research pharmacist will determine assignment based on a random number sequence.

Randomization. Randomization will occur in blocks of four based on a random number generator.

Blinding. Research subjects, clinicians, and research personnel will be blinded. To assess the success of blinding, which may be threatened by the occurrence of certain medication side-effects unique to particular

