## IV lidocaine v. hydromorphone for acute abdominal pain. A randomized trial. Version date 07112018

arms of the trial, research subjects and research personnel will be asked, at the time of ED discharge, to guess which medications were administered.

**Stratification.** Subjects will be stratified by study site (Moses or Einstein) and diagnosis (presumptive diagnosis of kidney stones versus non-kidney stone presumptive diagnosis). The rationale for stratification based on presumptive diagnosis of kidney stones is two-fold: 1) kidney stones represent a large subset of abdominal pain diagnoses; 2) kidney stones may be more likely to respond to IV lidocaine than other causes of abdominal pain

**Details of protocol.** Patients who present to our ED with acute abdominal pain will be referred by the attending emergency physician to the research staff for enrollment. Because of the severity of pain, only those who can appropriately make an informed decision about participating will be enrolled (those who cannot will be screened and excluded). Eligibility will be ascertained by research associates and verified by the site investigator. An EKG will be performed and interpreted by the attending physician. A point-of-care urine pregnancy test will be performed. Capacity to consent to participate in this study will be assessed by the attending emergency physician and documented. Masked medication will be obtained from the pharmacy. The research associate will perform a baseline pain assessment. Prior to the administration of any medication, patients will be placed on a cardiac monitor with telemetry where they will have continuous measurement of their heart rate and oxygenation. Blood pressure will be measured every 15 minutes for the first hour. The ED nurse will administer the research medication as described above. Research associates will perform an assessment of pain and adverse events every 30 minutes. Use of off-protocol medication to treat pain or associated symptoms will be recorded. Seven days after enrollment, patients will be contacted by telephone to determine satisfaction with the medication, course of pain subsequent to the ED visit, and occurrence of any adverse events.

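### One fixed block size of four, stated in the protocol, is an avoidable leak in concealment if blinding is imperfect; varying the size is a cheap, modest improvement

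*Combined protocol and SAP*

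**What the plan says.** In the combined protocol and SAP, Methods, the Randomization paragraph reads: "Randomization will occur in blocks of four based on a random number generator". The ratio is set under Investigational medications ("Patients will be randomized in a 1:1 ration to one of the following study arms"), so each block holds two assignments to each drug. Nothing says that the size varies or is withheld from site staff.

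Several safeguards are stated. On assignment: "Will be concealed. The research pharmacist will determine assignment based on a random number sequence". On blinding: "Research subjects, clinicians, and research personnel will be blinded". On supply, under Details of protocol: "Masked medication will be obtained from the pharmacy".

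The Blinding paragraph also says that the success of blinding is something "which may be threatened by the occurrence of certain medication side-effects unique to particular" arms. For that reason "research subjects and research personnel will be asked, at the time of ED discharge, to guess which medications were administered".

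Under Details of protocol, patients "will be referred by the attending emergency physician to the research staff for enrollment". Research associates then establish eligibility, with verification by the site investigator, and the same role assesses pain and adverse events every half hour. The Stratification paragraph names two sites and two presumptive diagnosis groups, which makes four strata, two at each site.

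**The concern.** A pharmacist-held list and masked supply hide the next assignment directly. They do not stop someone inferring it from earlier patients in a block of known size. The information could come from the side effects that the plan itself mentions, and the people placed to see them include those who screen the next patient. Someone with a view on the next assignment may, even without intending it, be readier to approach some patients than others. The primary analysis is an unadjusted difference in mean improvement and would not correct for that.

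**Working it through.** **The plan's own figure.** The plan gives no figure for predictability. Its sample size reproduces by the normal approximation: 2 × (1.960 + 0.842)² × 2.8² / 1.3² = 72.8, so 73 per group. Then 146 × 1.05 = 153.3, so 154 in total.

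**Inputs.** From the protocol: blocks of four, 1:1, four strata. Assumed: each stratum has its own list, the observer knows the block size and where blocks begin, and each earlier patient's drug is identified correctly with probability q. The documents give no q, so the range 0.5 (blinding intact) to 1.0 (fully lost) is shown.

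**Fixed blocks of four, exact.** The six possible blocks are equally likely. The best guess is right with these probabilities:

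- First patient: 1/2.
- Second: the opposite drug follows with probability 2/3 if the first was identified correctly and 1/3 if not, so q × 2/3 + (1 − q) × 1/3 = (1 + q)/3.
- Third: guess the other drug if the first two look alike, otherwise toss a coin. This also averages (1 + q)/3.
- Fourth: guess the drug seen less often so far. This is right if both patients on the more frequent drug were identified correctly, or if one of them was and the patient on the other drug was misread: q² + 2q(1 − q)².

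At q = 0.8: (0.500 + 0.600 + 0.600 + 0.704)/4 = 0.601.

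**Varying sizes.** These were simulated for an observer who knows the set of possible sizes (4, 6 and 8, equally likely) and updates by Bayes' rule, with 40 patients per stratum assumed.

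| q | 2nd and 3rd patient | 4th patient | Mean, fixed four | Mean, sizes 4/6/8 |
|---|---|---|---|---|
| 0.5 | 50.0% | 50.0% | 50.0% | 50% |
| 0.6 | 53.3% | 55.2% | 53.0% | about 52% |
| 0.7 | 56.7% | 61.6% | 56.2% | about 54% |
| 0.8 | 60.0% | 70.4% | 60.1% | about 57% |
| 0.9 | 63.3% | 82.8% | 64.9% | about 60% |
| 1.0 | 66.7% | 100% | 70.8% | about 68% |

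**Confident guesses.** With fixed fours and q = 1.0, the fourth assignment is always certain and the third is certain in one block of three: (0 + 0 + 1/3 + 1)/4 = 33%. With 4/6/8 this is about 2%. For q below 1, no assignment is ever certain. Assignments predictable with at least 80% confidence fall from about 35% to almost none at q = 0.9, and from about 4% to none at q = 0.8.

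**Possible effect on the estimate (illustration).** Suppose staff act on every guess and shift the enrolled patient's expected improvement by d points in the guessed direction. With p the proportion of correct guesses, the bias is 2d(2p − 1). For d = 0.5 and q = 0.8, this is 2 × 0.5 × 0.20 = 0.20 points with fixed fours (p = 0.60) and 2 × 0.5 × 0.14 = 0.14 with 4/6/8 (p = 0.57). For d = 0.1 the figures are 0.04 and 0.03. For comparison, the target difference is 1.3 and the standard error is 2.8 × √(2/73) = 0.46.

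**Cost in balance.** With assumed stratum sizes of 62, 61, 16 and 15, the largest simulated overall imbalance was 4 patients with fixed fours and 8 with sizes 4/6; it was also 8 with 4/6/8. The 95th percentile was 4 in every case. Power is 0.801 at 73 against 73 and 0.800 at 77 against 69. The outer limit is half the largest block in each of four strata: 4 × 2 = 8 for fixed fours and 4 × 4 = 16 for 4/6/8. At 81 against 65, 1.3/(2.8 × √(1/81 + 1/65)) − 1.96 = 0.83, which is power of about 0.80.

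**The case against.** The strongest reply is that this is not an open-label trial, where fixed small blocks would be a serious flaw. Staff are blinded, supply is masked, the pharmacist holds the list, and the plan checks blinding at discharge. With blinding intact the best guess is right exactly half the time. Using the block structure also means following enrolment order and likely drug within each site-by-diagnosis list. Nothing in the protocol says that the block size is taught to enrolling staff, or that the same attending physicians see successive patients. All of this stands, and it keeps the point small.

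It does not remove the point. The block size is in the protocol, each site has only two strata, and the overlap between screening and adverse-event assessment is written into the research associate's role. Asking research personnel to guess the drug also prompts them to form a view.

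A reader might infer that the plan expects side effects to reveal the drugs. It does not say so: it says that blinding may be threatened, and it measures this. A reader might also infer that staff can often predict the next assignment. The documents do not support that: at 70% to 80% accuracy the guess is right 56% to 60% of the time, and anything close to frequent prediction requires blinding to be largely lost.

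**Conclusion.** The point holds as a minor, preventive improvement, not as an error. No passage contradicts another, and sample size and analysis are unaffected. A fixed, disclosed block of four leaks information only if blinding is imperfect; the best guess then rises from 50% to between 53% and 71% over the assumed accuracy range. Varying sizes lowers the average by about 1 to 5 percentage points. The clearer benefit is that confident guesses largely disappear when blinding is partly lost. If blinding fails completely, certainty becomes rare, but the average guess is still right about 68% of the time, so varying the sizes does not replace sound masking.

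The result rests on four assumptions that the documents do not settle: identification accuracy, separate lists per stratum, staff knowledge of the block size, and patients per stratum. It would go too far to say that selection bias is present, since the documents show only a route for it. It would also go too far to call the change entirely free, because the possible imbalance grows slightly.

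**What to change.** Have the research pharmacist generate a separate list for each stratum with block sizes drawn at random, for example from 4, 6 and 8. Keep the sizes in a document held by the pharmacist and not available to enrolling staff. In the Randomization paragraph, replace the statement of blocks of four with permuted blocks of varying size, within site and presumptive diagnosis.

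The cost is one setting in the list generator and one sentence. Sample size stays at 73 per group and 154 in total. The only downside is the slightly larger possible end-of-list imbalance, with a negligible effect on power. The treatment guesses already planned for discharge will show how accurately research personnel identify the drug, which is the quantity assumed here, so they should be reported.

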## IV lidocaine v. hydromorphone for acute abdominal pain. A randomized trial. Version date 07112018

arms of the trial, research subjects and research personnel will be asked, at the time of ED discharge, to guess which medications were administered.

**Stratification.** Subjects will be stratified by study site (Moses or Einstein) and diagnosis (presumptive diagnosis of kidney stones versus non-kidney stone presumptive diagnosis). The rationale for stratification based on presumptive diagnosis of kidney stones is two-fold: 1) kidney stones represent a large subset of abdominal pain diagnoses; 2) kidney stones may be more likely to respond to IV lidocaine than other causes of abdominal pain

**Details of protocol.** Patients who present to our ED with acute abdominal pain will be referred by the attending emergency physician to the research staff for enrollment. Because of the severity of pain, only those who can appropriately make an informed decision about participating will be enrolled (those who cannot will be screened and excluded). Eligibility will be ascertained by research associates and verified by the site investigator. An EKG will be performed and interpreted by the attending physician. A point-of-care urine pregnancy test will be performed. Capacity to consent to participate in this study will be assessed by the attending emergency physician and documented. Masked medication will be obtained from the pharmacy. The research associate will perform a baseline pain assessment. Prior to the administration of any medication, patients will be placed on a cardiac monitor with telemetry where they will have continuous measurement of their heart rate and oxygenation. Blood pressure will be measured every 15 minutes for the first hour. The ED nurse will administer the research medication as described above. Research associates will perform an assessment of pain and adverse events every 30 minutes. Use of off-protocol medication to treat pain or associated symptoms will be recorded. Seven days after enrollment, patients will be contacted by telephone to determine satisfaction with the medication, course of pain subsequent to the ED visit, and occurrence of any adverse events.

### Measures

- 1) Pain intensity will be measured using a verbal numerical scale of which 0 represents no pain and 10 represents the worst pain imaginable
- 2) Medication preference. Preference for a specific medication is a highly patient centered outcome, in which an individual determines for herself the benefit of a particular drug versus the adverse effects experienced. We will include in this study a measure that has been used in multiple ED-based trials—"The next time you come to the ER for treatment of abdominal pain, do you want to receive the same medication again?" Patients will be asked to choose among the following responses: "Yes," "No," or "Not sure"
- 3) Side effects. We will use the following question: "Did you have any new symptoms that began only after you got the study medication?" An affirmative response will be followed by an open-ended question eliciting details.

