### Secondary efficacy outcomes.

- 1) Sufficient pain relief, defined as no need for off-protocol parenteral pain medication during the ED visit. The following parenteral medications will be considered off protocol pain medication: any opioid, any non-steroidal anti-inflammatory drug
- 2) Improvement in numerical pain scores 15, 30, 90, 120, and 180 minutes after investigational medication

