## IV lidocaine v. hydromorphone for acute abdominal pain. A randomized trial. Version date 07112018

administration

- 3) Patient preference for the medication they received.
- 4) Need for medication to treat associated symptoms such as anti-nausea medication or an anti-histamine

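### The preference question does not say which drug it means, so some patients given another analgesic may answer about that drug; a minor wording fix to a secondary outcome

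*Combined protocol and SAP*

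**What the plan says.** Measures, item 2, gives the exact question: "The next time you come to the ER for treatment of abdominal pain, do you want to receive the same medication again", with the answers 'Yes', 'No' or 'Not sure'. The same item explains the purpose: "Preference for a specific medication is a highly patient centered outcome", in which the patient weighs a drug's benefit against its adverse effects. The item is described as having been used in several earlier ED trials. Secondary efficacy outcomes, item 3, lists the result as "Patient preference for the medication they received".

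The next item in Measures, on side effects, does identify the drug: "Did you have any new symptoms that began only after you got the study medication".

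Some patients will receive more than one drug. Under Investigational medications: "Patients who require additional medication beyond one hour will be administered medication at the discretion of the treating clinician". Secondary efficacy outcomes, item 1, defines off-protocol parenteral pain medication as "any opioid, any non-steroidal anti-inflammatory drug". The Analysis section keeps every patient whose study infusion was started, including those who ask for off-protocol analgesia.

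No section says when the preference question is asked. The nearest statement, under Details of protocol, is "Seven days after enrollment, patients will be contacted by telephone to determine satisfaction with the medication". That contact falls after any rescue in the ED, and it too leaves the medication unspecified.

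**The concern.** The question is worded as if each patient received one medication. A blinded patient who had little relief from the drip and good relief from a later injection can honestly say 'Yes' with the later injection in mind, and is then counted as preferring the study drug. Nothing in the plan tells the interviewer which drug is meant or how such answers are to be handled.

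The error can arise only in patients who received another drug, who will mostly be those in whom the study drug gave too little relief. If they are more numerous in one arm, the error is unequal between arms. A finding of similar preference would then be hard to interpret, on an outcome that the plan presents as strongly patient-centred.

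**Working it through.** **1. Does another section settle which drug is meant?** The side-effect item names the study medication; the preference item and the outcome list do not. The 30-minute question, "Do you want another dose of the same medication to treat your pain", uses similar wording, but it comes before the discretionary period, when the investigational drug is the only protocol drug given so far. It does not settle what a patient understands after rescue.

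**2. The plan's own figure.** The documents give no figure for preference. Their sample size concerns the pain score: 2 × (1.960 + 0.842)² × 2.8² / 1.3² ≈ 72.8, so 73 per arm, and 146 × 1.05 = 153.3, so 154. This reproduces the plan and has no bearing on the present point.

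**3. Inputs for an illustration.** All are assumptions, since the documents give no such rates.
- *r*, share rescued: 20% (hydromorphone) and 40% (lidocaine)
- *y*, 'Yes' rate without rescue: 75% in both arms
- *q*, 'Yes' rate of rescued patients about the study drug: 10%
- *s*, their 'Yes' rate about the rescue drug: 50% to 70%
- *m*, share of rescued patients who answer about the rescue drug: 0 to 1

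**4. Formula.** Observed 'Yes' rate in an arm = (1 − r)y + r[(1 − m)q + ms].

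True rates (m = 0):
- Hydromorphone: 0.8 × 0.75 + 0.2 × 0.10 = 0.62
- Lidocaine: 0.6 × 0.75 + 0.4 × 0.10 = 0.49
- Difference: 13 points

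With *q* and *s* the same in both arms, the observed difference is the true difference minus m × (r_L − r_H) × (s − q). At full misattribution the loss is 0.20 × 0.40 = 8 points for s = 50%, and 0.20 × 0.60 = 12 points for s = 70%.

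| Share misattributing (m) | s = 50% | s = 70% |
|---|---|---|
| 0 | 13 points | 13 points |
| 0.25 | 64% v 53%: 11 points | 65% v 55%: 10 points |
| 0.5 | 66% v 57%: 9 points | 68% v 61%: 7 points |
| 1 | 70% v 65%: 5 points | 74% v 73%: 1 point |

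**5. A second set of assumptions** (y = 75%, q = 20%, s = 65%; m = 0, 0.5 and 1).
- Rescue 15% v 30%: 8.3, 4.9 and 1.5 points
- Rescue 20% v 40%: 11.0, 6.5 and 2.0 points
- Rescue 25% v 50%: 13.8, 8.1 and 2.5 points

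In the middle case the loss is 4.5/11.0, about 40%, if half misattribute, and 9.0/11.0, about 80%, if all do.

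**6. Direction.** The loss term is positive when the less-preferred arm has more rescue and the rescue drug is liked better than the study drug. It is zero when rescue rates are equal and *q* and *s* are common to both arms. If exactly one of the two conditions is reversed, the difference is widened instead.

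**The case against.** The intended drug is clear to anyone reading the protocol. The item is introduced as preference for one particular drug, and the 30-minute question uses similar wording for the investigational drug. A patient who is unsure which drug is meant can say 'Not sure', a response that the illustration does not model. A drug that needs more parenteral opioid or NSAID rescue would also show this in secondary outcome 1, beside the preference result. These points stand as reasons to expect partial rather than wholesale misreading. They do not remove the ambiguity: the patient hears the question and not the protocol, earlier use does not show how rescued patients understood it, and the rescue outcome does not correct an individual answer.

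A reader might infer that the outcome is bound to be pulled toward no difference, or that a 13-point difference would shrink to 5 or 1. The documents support neither. The direction needs both conditions in step 6, and the documents establish neither of them. The 5-to-1 figures need every rescued patient to answer about the rescue drug.

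A reader might also infer that the main answer must be taken at 60 minutes, before discretionary analgesia opens. That does not follow either. A second infusion started at 30 minutes and run over 10 ends at 40, so the question would come only 20 minutes later. An early answer also cuts short the weighing of benefit against adverse effects that the item is meant to capture. Naming the drug deals with the ambiguity without this cost.

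**Conclusion.** The concern holds as a minor point. The scripted question leaves the drug unspecified, the plan allows other analgesics after one hour and keeps those patients in the analysis, and no section resolves which drug is meant. Some rescued patients may therefore be misclassified.

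Whether this narrows the difference between arms, and by how much, cannot be known from the documents. On the first set of assumptions, a true 13-point difference would be seen as 11 to 10 points with a quarter of rescued patients misattributing, and 9 to 7 with half. The larger losses are an upper bound within those assumptions. The effect is confined to one secondary outcome; the primary outcome and the sample size do not change.

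**What to change.** In the scripted question, replace the reference to the same medication with: *the same study medication, the one given by drip when you joined the study*. This brings it into line with the side-effect item. It keeps the blind, because both drugs are given by drip and neither is named.

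Report the preference answers by whether off-protocol analgesia was given, as a descriptive display beside the comparison of all analysed patients; rescue occurs after randomization, so the subgroups are not a randomized comparison. Details of protocol already has off-protocol medication recorded, so no new data are needed. No change of time point is needed for this purpose.

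The cost is a few words in the script and slightly less comparability with the earlier ED trials that used the item.

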### Safety endpoints

- 1) Frequency of development of any new symptom after administration of the investigational medication
- 2) Frequency of requirement of naloxone
- 3) Frequency of a change in the disposition of the patient attributable to investigational medication
- 4) Frequency of missed diagnosis, defined as an unplanned return visit to the ED resulting in hospital admission

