### Analysis.

Baseline characteristics will be reported as mean (SD), median (IQR), or n/N (%), as appropriate. The primary outcome, improvement in 0-10 pain score between baseline and one hour will be reported as mean (95%CI) for each group. The between-group difference in mean improvement in 0-10 pain score will be calculated with 95%CI. If this 95%CI does not cross zero, the results will be considered statistically significantly different. All dichotomous values will be reported as proportions with 95%CI. For formal statistical testing, we will use the ttest.

We will use an intention to treat analysis. Once an investigational medication is initiated, the patient will be included in the analysis, regardless of whether or not the patient completed the medication infusion and regardless of whether or not the patient requests off-protocol analgesic medication.

**Data collection and processing.** Data acquisition will be performed using REDCap (Research Electronic Data Capture), a secure, web-based application designed specifically to support data capture for research studies. The REDCap project (<http://project-redcap.org/>) is an international project, with more than 70 institutional partners from CTSA and GCRC funded institutions. Paper consent documents will be maintained in locked research cabinets.

**Data monitoring committee and interim analysis.** This committee will be headed by [name], PhD, an epidemiologist and include [name], MD, the director of the Moses ED. The committee will meet every month with the PI to 1) monitor adverse events and develop strategies to minimize these; and, 2) monitor recruitment and enrollment. Because our goal is to report the results with sufficient precision to influence clinical practice, we will not perform an interim efficacy analysis.

**Registration.** The study will be registered at <http://www.clinicaltrials.gov>.

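### Safety endpoint 1 counts only symptoms that started after the drug, so worsening of a symptom already present is missed there and not reliably captured by any other named endpoint

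*Combined protocol and SAP*

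**What the plan says.** The aim, stated at the end of the Background, covers safety as well as efficacy: "To determine the relative efficacy and safety of IV lidocaine among patients with acute abdominal pain".

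- **Measures, item 3** asks "Did you have any new symptoms that began only after you got the study medication". Then: "An affirmative response will be followed by an open-ended question eliciting details".
- **Safety endpoints, item 1** matches it: "Frequency of development of any new symptom after administration of the investigational medication".
- **Details of protocol** names pain as the only baseline assessment by the research associate. It then states "Research associates will perform an assessment of pain and adverse events every 30 minutes". At the 7-day call, patients are asked about satisfaction, "course of pain subsequent to the ED visit, and occurrence of any adverse events". Neither check has stated wording.
- **Secondary efficacy outcomes, item 4** is "Need for medication to treat associated symptoms such as anti-nausea medication or an anti-histamine".
- **Analysis** says "All dichotomous values will be reported as proportions with 95%CI". It names a between-group difference for the pain score but none for safety.

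**The concern.** Patients with acute abdominal pain may already be nauseated or light-headed before any study drug, and secondary outcome 4 shows that the plan expects associated symptoms. When a drug effect resembles a symptom of the illness, patients who came in with that symptom can register the effect only as worsening. The side-effect question does not ask about worsening, and its open-ended follow-up opens only after a yes. These patients count as event-free for that symptom. Without a baseline symptom record, the worsening cannot be reconstructed later.

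At stake is how the safety result can be read. A comparison of new symptoms alone could be taken as a comparison of all symptomatic harm, and the two can differ.

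**Working it through.** **The plan's own figure.** With SD 2.8, difference 1.3, two-sided alpha 0.05 and power 0.80: 2 × (2.8 × (1.960 + 0.842) / 1.3)² = 72.8, so 73 per group. Then 146 × 1.05 = 153.3, so 154 in total, or 77 per arm. This reproduces. It concerns pain only; the documents give no rate of baseline, new or worsened symptoms.

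**Where worsening could be recorded.**

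- Side-effect question and safety endpoint 1: excluded by wording.
- Secondary outcome 4: only if medicated, and it does not separate nausea that the drug worsened from nausea that would have been treated anyway.
- 30-minute checks: possible, but the only worded instrument is the new-symptom question.
- 7-day call: possible, but with no definition, a week's recall and no named endpoint for the answers.
- Naloxone, changed disposition and return visit with admission: not symptom measures.

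**Direction of the effect, one symptom.** Let b be the share with the symptom at entry, n₁ and n₂ the risks of new onset among those without it, and w₁ and w₂ the risks of worsening among those with it.

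- Recorded difference = (1 − b)(n₂ − n₁)
- New-or-worsened difference = (1 − b)(n₂ − n₁) + b(w₂ − w₁)

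The gap is b(w₂ − w₁), so everything turns on the worsening risks. All rates below are assumptions, with b = 20%, 40%, 60%:

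| Pattern (arm 1 v arm 2) | Recorded difference, points | New-or-worsened difference, points |
|---|---|---|
| New 10% v 25%, worsened 10% v 25% | 12, 9, 6 | 15, 15, 15 |
| New 10% v 25%, worsened 17.5% in both | 12, 9, 6 | 12, 9, 6 |
| New 10% v 25%, worsened 25% v 10% | 12, 9, 6 | 9, 3, −3 |
| New 15% in both, worsened 10% v 25% | 0, 0, 0 | 3, 6, 9 |

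Rows 1 and 4 shrink the difference, row 2 leaves it unchanged and row 3 exaggerates it. On the ratio scale, row 1 keeps 2.5 throughout. In row 2 the recorded ratio is 2.5 against 2.04, 1.69 and 1.41 for new or worsened.

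**Size when worsening mirrors new onset.** Assume risk q = 25% v 5%, whether or not the symptom was present at entry, with 77 per arm. Power = Φ((d − 1.96·SE₀)/SE₁), where SE₀ is pooled and SE₁ unpooled.

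| b | Recorded (1 − b)q | Difference, points | Power |
|---|---|---|---|
| 0% | 25% v 5% | 20 | 94% |
| 40% | 15% v 3% | 12 | 74% |
| 60% | 10% v 2% | 8 | 55% |

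Endpoint 1 is any new symptom, so add an assumed 30% background of unrelated new symptoms in both arms: p = 1 − 0.7 × (1 − (1 − b)q).

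| b | Recorded p | Difference, points | Ratio | Power |
|---|---|---|---|---|
| 0% | 47.5% v 33.5% | 14 | 1.42 | 42% |
| 40% | 40.5% v 32.1% | 8.4 | 1.26 | 19% |
| 60% | 37.0% v 31.4% | 5.6 | 1.18 | 11% |

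**A mitigating case.** Without background, suppose half of the affected patients with the symptom at entry also develop a different new symptom and so answer yes. The recorded risk is q(1 − 0.5b). The difference is then 16 points at b = 40% and 14 at b = 60%, with power 87% and 82%.

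**Would a single merged count be better?** Suppose the illness itself worsens the symptom in a share w of those who have it, in both arms. The merged risk is (1 − b)q + b(1 − (1 − w)(1 − q)). With w = 50% and no background it is 40% v 24% at b = 40% (power 57%) and 47.5% v 33.5% at b = 60% (power 42%). Both fall below the 74% and 55% of the new-only count. With w = 20% the merged count does better than the new-only count.

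**The case against.** The question and endpoint 1 agree with each other, and the question is the same in two blinded arms. Dating symptoms by onset after dosing is a defensible way to separate drug effects from the presenting illness. Adverse events are assessed every 30 minutes and at 7 days, the monitoring committee reviews them monthly, treated symptoms enter secondary outcome 4, and the preference question is described as weighing benefit against adverse effects, with no limit to new ones. A patient with nausea at entry who becomes newly dizzy or drowsy is still counted. The trial is sized on pain, so power for safety is not a planned property.

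Much of this stands. The new-symptom comparison is valid for what it defines. A reader might infer that worsening is not captured at all; the documents do not support that, because the other routes could pick some of it up. A reader might also infer that the safety comparison is biased toward no difference. That follows only if the drug that causes more new symptoms also worsens more existing ones, and the documents give no rates to establish it.

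What does not stand is that the other routes close the gap. None is stated to count worsening, none feeds a named endpoint for untreated worsened symptoms, and no baseline symptom record is named.

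**Conclusion.** The point holds as a limit on what safety endpoint 1 can answer. Drug-related worsening of an existing symptom falls outside it and is not reliably captured by any other named endpoint, although relative safety is part of the aim.

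The size is not estimable from the documents. Under one assumed pattern a 20-point difference is recorded as 12 or 8 points; under others it is unchanged or exaggerated. The new-only result should therefore not be read as overall symptomatic safety. The primary outcome, sample size and efficacy conclusion are not affected. The change is worth making before enrolment, because symptom status at entry cannot be reliably recovered afterwards.

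**What to change.** Keep the new-symptom question and safety endpoint 1 as they are, and add three things:

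1. In Measures, item 3, a second question: *Did any symptom you already had get worse after you got the study medication?* Use the same open-ended follow-up.
2. In Details of protocol, have the research associate tick the symptoms present (nausea, vomiting, dizziness, drowsiness, itching) when taking the baseline pain score.
3. In Safety endpoints and Analysis, report 'worsened' and 'new or worsened' by arm, with the between-arm difference and 95% CI, beside the new-only count.

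The cost is a few extra form items. Some worsening from the underlying illness will be counted in both arms and adds noise, which is why the new-only endpoint stays and is not replaced by a merged count.
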